## 1.1. Study Schematic: On-study Participant Progression

\*NOTE: Release from quarantine is foreseen at Day 8 (8 days post-inoculation) in case no virus is detected by qualitative virus antigen test or polymerase chain reaction (PCR) (negative virus antigen test or PCR below Ct cut-off) and the participant has no clinically significant symptoms. If the participant continues to have clinically significant symptoms and/or detectable virus on Day 8, additional extended quarantine stay may be required at the discretion of the Investigator.

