Serum beta-human chorionic gonadotrophin (β-HCG) pregnancy test (i)		>	۲°													(X)
Human immunodeficiency virus (HIV), Hepatitis A, B, and C tests	х															
Haematology (j)	Х	>	۲°				Xd		Х				Х	(X)	Х	X
Biochemistry (j)	х	>	۲°						Х				Х	(X)	Х	Х
Coagulation (j)	Х	>	( °				Xd		Х				Х	(X)		Х
Cardiac enzymes	х	)	۲°						х	1			Х			
Thyroid function test	х	()	<)°									1				
Blood - immune markers (k)	Х	X°	X	х			Xq	х	х	х	Х	Х	Х	х	Х	Х
Blood – transcriptomics markers			BD	х		х	BDq	BD	BD	BD	BD	BD	BD	х		

	Screening		QUARANTINE ISOLATION									Γ	Early				
Study phase >	phase*	Admission to quarantine		Human viral challenge (HVC)					Post	HVC da	iys	Discharge	Clinic visit		withdrawal visit		
Study day →	Day -56 (Day -90 for	Day	Day		Day 0		Day	Day	Day	Day	Day	Day	Day	Day	Follow-up		
Procedure V	influenza serology) to Day -3	-2	-1	Pre	Challenge	Post	1	2	3	4	5	6	7	8	Day 28 (± 3 days)		
Blood – deoxyribonucleic acid (DNA) - genomics		>	۲°														
Blood - Pharmacokinetics (PK)		>	۲°				2X t	Х		Х		Х		Х	Х		Х
Blood - anti-drug antibodies (ADA)		>	۲°				2X t	х		Х		х		х	х		х
Collection of Respiratory Samples																	
Nasopharyngeal swab / nasal wash - Respiratory pathogen screen (I)	т	X°	(X) p														
Nasopharyngeal swab / nasal wash - Rapid viral antigen test or polymerase chain reaction (PCR)														(X) p			(X)
Nasopharyngeal swab / nasal wash – Virology (m) and exploratory research	т		x				BDq	BD	BD	BD	BD	BD	BD	х			х
Nasal sample (nasosorption / mid turbinate swab) – PK and exploratory immunology			х				Xď	x	Х	х	х	х	х	х			
Safety Assessments																	
Adverse events (n)	х		continuous							Х							
Concomitant medications (n)	Х							con	tinuous								Х

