# hvivo

CONFIDENTIAL

а	Study specific consent may occur on the day of admission, providing all required eligibility information has been collected through hVIVO Generic Screening process.
b	Only the applicable Inclusion / Exclusion criteria will be reviewed at each time point.
с	Height will be taken at Screening only.
d	Urine pregnancy tests will be performed in female participants of childbearing potential.
е	Vital signs will be taken at the same time(s) each day (±1 hour). On Day 1 the vital signs will be performed pre-infusion, and at 15 minutes, 30 minutes, 60 minutes, 90 minutes, 2 hours, 4 hours, and 8 hours after the start of the drug infusion.
f	Distribution of paper tissues and bags will start on Day -1, with the first collection on Day 0. Thereafter collection of tissues will occur at the same time points (±1 hour) with tissues distributed 24 hours ahead.
g	Assessments will be performed at the same time points (±1 hour) during quarantine.
h	A serum FSH test will be performed in all post-menopausal female participants.
i	Blood serum pregnancy test (β-hCG) will be performed in all female participants.
j	Blood may be drawn under non-fasted conditions. Repeat bloods may be drawn under fasted conditions if a lipid profile (triglyceride) or glucose is required (at Principal Investigators [PIs] discretion).
k	Blood will be collected for: i) virus serology (influenza antibody assay) to determine eligibility (at screening) and seroconversion (at Day -2 / -1 & Day 28), and ii) exploratory immune markers.
I	Nasopharyngeal swab or nasal wash for respiratory virus screen to assess for the presence of other respiratory viruses; if found positive the participant will not be eligible for the current quarantine.
m	Nasopharyngeal swabs (or nasal wash, if appropriate) will be collected for viral load assessments and exploratory immunology. Post inoculation nasal virology samples will be collected and used for qRT-PCR and viral culture assay.
n	Adverse events and concomitant mediations are reviewed throughout the study including pre- and post-infusion with IMP/placebo and pre- and post-inoculation.
0	Can be performed on Day -2 or Day -1. If admission at Day -1, all procedures scheduled for Day -2 can be performed on Day -1, as appropriate.
р	Optional and may be collected or not as per PI discretion for exploratory research.
q	Pre-infusion (only applicable to the first assessment on Day 1).
r	Post-dose ECG.

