s	An exploratory wearable may be used to capture continuous measures parameters such as: HR, heart rate variability, SpO 2 , temperature, ECG. This may include a period of up to 4 weeks prior to quarantine admission and up to 4 weeks post discharge from quarantine.
t	PK and ADA samples to be taken on Day 1 (IMP / placebo administration day): one sample pre-infusion and one sample at 1-hour post-infusion end (infusion end includes any time required for flushing).
Notes:	Parenthesis indicates the assessment may be optional, or at the PI's discretion. For all participants TDS assessments will commence on Day 0, the first assessment will be pre-virus challenge. The PI may perform additional safety assessments as required. Where any nasal sampling time points occur together, the order of sampling will typically be (1) nasosorption, (2) nasopharyngeal swab followed by (3) nasal wash

GENOMIC, TRANSCRIPTOMIC AND PROTEOMIC SAMPLES									
	Yes 🛛 No								
Deoxyribonucleic acid (DNA) / ribonucleic acid (RNA) / proteomic sample collection:									
Consent considerations:	Genetic consent. Future use of remaining samples for exploratory research: blood samples (including processed blood) and respiratory samples for biomarker analysis relevant to the exploratory objectives of the study.								

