Influenza A/California/2009 H1N1 virus infection and severe complications	Approximately 65% chance of becoming infected with Influenza A/California/2009 H1N1 virus (Sloan et al. 2020). Typical Influenza A/California/2009 H1N1 virus illness: abrupt onset of rhinitis, nasal stuffiness, fever, malaise, myalgia (muscle aches), and sore throat. Influenza, like many viruses, can cause more substantial health issues such as myocarditis (inflammation or damage to the heart muscle). However, the chance of this resulting in serious or permanent changes is rare, as most cases are minor and resolve without any lasting changes.	The safety profile of this batch of Influenza A/California/2009 H1N1 virus has been used for over 5 years by several groups globally. At hVIVO over 100 participants have been challenged with a different batch of Influenza A/California/2009 H1N1 virus. Influenza A/California/2009 H1N1 virus infection in healthy adults usually resolves without treatment within 3 to 7 days (Sloan et al. 2020). Strict inclusion and exclusion criteria will apply to ensure only healthy adults are enrolled in this study. There will be a daily medical monitoring in a Quarantine Unit for at least 8 days post-challenge. Qualified medical and nursing staff in the Quarantine Unit will monitor for and manage any symptoms. Participants will be closely followed up while being in quarantine. Electrocardiogram (ECG) will be performed, and cardiac enzymes will be tested at least 3 days, and 7 days post-viral challenge.
	Transient increase in alanine aminotransferase (ALT) or aspartate aminotransferase (AST) without clinical presentation, with a good prognosis upon improvement of infection.	ALT and AST will be monitored.
Transmission of Influenza A/California/2009 H1N1 virus to participants' close contacts	Influenza A/California/2009 H1N1 virus presence in nasal secretions can cause infection in close contacts.	Virus is usual absent from the nose by the time participants are discharged from quarantine. This will be confirmed by testing a nasal swab sample using by a qualitative virus antigen test or polymerase chain reaction (PCR) to determine

Potential Risk of Clinical Significance	Rationale for Risk	Mitigation Strategy						
		participants' suitability for departure.						
		In addition, participants will be instructed to avoid close contact with vulnerable people as described in Section 2.3.1.4 for two weeks after they leave the Quarantine Unit.						

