#### 8.17.2. Rapid Influenza Discharge Test

A rapid viral antigen test will be used to determine the presence of influenza only in a nasopharyngeal swab (or nasal wash) sample taken prior to discharge from the Quarantine Unit on Day 8. A qualitative PCR screening test may be used as an alternative test for this purpose.

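### The Schedule of Activities marks the Day 8 rapid antigen/PCR test as optional and exploratory, while Sections 1.1, 2.3.1.3 and 8.17.2 treat it as part of discharge from quarantine

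*Combined protocol and SAP*

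**What the plan says.** The Schedule of Activities has a respiratory-sample row headed "Nasopharyngeal swab / nasal wash - Rapid viral antigen test or polymerase chain reaction (PCR"). Its only entry during quarantine is on Day 8, printed as (X) with superscript p. Two notes to the schedule explain that marking. Footnote p reads "Optional and may be collected or not as per PI discretion for exploratory research". The general note reads "Parenthesis indicates the assessment may be optional, or at the PI's discretion".

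Three other places describe the same test:

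- **Section 8.17.2, Rapid Influenza Discharge Test:** "A rapid viral antigen test will be used to determine the presence of influenza only". The sample is taken before Day 8 discharge, and a qualitative PCR may be used instead.
- **Section 2.3.1.3, Table 1, transmission to close contacts:** after stating that virus has usually gone by discharge, the mitigation column says "This will be confirmed by testing a nasal swab sample using by a qualitative virus antigen test" or PCR. The stated aim is to judge whether the participant is fit to leave.
- **Section 1.1, note to the schematic:** "Release from quarantine is foreseen at Day 8 (8 days post-inoculation) in case no virus is detected by qualitative virus antigen test" or PCR, together with an absence of clinically significant symptoms.

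Section 4.1 states discharge on Day 8, or later at the Principal Investigator's discretion, and mentions no test.

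**The concern.** Table 1 names spread of the challenge virus to contacts as a risk and offers this test as one of the mitigations. The risk falls on people outside the trial, including the vulnerable contacts listed in Section 2.3.1.4. If the test may be left out at discretion, and is collected for research, then the operational table does not secure the safeguard that the risk table describes. Anyone reading the risk assessment would believe that absence of virus is confirmed before departure, while staff working from the schedule would have no such instruction.

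**Working it through.** The protocol states no figure on this point and no formula applies. The check is a comparison of passages.

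1. **Does footnote p belong to the Day 8 discharge test?** Take the procedure name as column 0 and screening as column 1; Day 1 is then column 7 and Day 8 column 14. The entry with superscript p is in column 14, the same column as the Day 8 virology entry. The attachment is not an artefact of a broken table.

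2. **Status of the test.** The schedule marks it optional in two independent ways: the parentheses and the footnote. Section 8.17.2 and Table 1 state it without any option. Section 1.1 presupposes a result, because Day 8 release is foreseen where none of the virus is detected.

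3. **Purpose of the test.** Footnote p gives exploratory research. Section 8.17.2 gives detection of influenza before discharge, and Table 1 gives suitability for departure. These are not the same purpose.

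4. **Which text governs?** Section 8 describes the schedule as a summary of procedures and timing, but also says that adherence to what it specifies is essential and required. It does not rank the schedule above or below the section text, and no other section does. Omitting the test therefore complies with the schedule and departs from Sections 1.1, 2.3.1.3 and 8.17.2.

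5. **Does another sample fill the gap?** A virology swab is scheduled on Day 8 without parentheses, after twice-daily virology swabs on Days 1 to 7. Footnote m assigns the post-inoculation virology samples to qRT-PCR and culture. Section 7.5 has the Principal Investigator and the sponsor's medical expert review available virology data as appropriate during quarantine. No text says that the Day 8 virology result is available before release, or that it is used to decide release.

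6. **What follows from a positive result?** Section 1.1 says that with continuing symptoms or detectable virus an "additional extended quarantine stay may be required at the discretion of the Investigator". Retention is therefore not automatic even when the test is done.

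**The case against.** The strongest reply is that Section 8.17.2 binds the site as much as the schedule does, so a site that skipped the test would breach the protocol. That stands: the documents conflict, and they do not clearly permit omission. It does not remove the need to reconcile them, because staff can follow one text only by departing from the other.

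A copied superscript is also plausible. Footnote p appears as well on the optional Day -1 respiratory pathogen screen. The documents cannot settle this, and the parentheses would still mark the Day 8 test as optional.

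Several stronger readings are tempting, and the documents do not support them:

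- **Release depends on the test in three sections.** Only Section 1.1 and Table 1 link the result to release. Section 8.17.2 requires the test but sets no release condition.
- **Participants could leave untested.** The Day 8 virology swab is not optional. What can be missing is the discharge test.
- **There is the same contradiction at early withdrawal.** The test is also (X) at that visit, but no section requires it there. Virology is a plain X at that visit, and Section 7.1 asks for the listed tests wherever possible and for counselling on transmission.
- **About 39 participants are at issue.** Table 1 puts infection at about 65%, and 0.65 × 60 = 39 if SAB-176 has no effect on infection. That counts participants infected at any time, not those shedding on Day 8. Table 1 says infection usually resolves within 3 to 7 days.
- **The test is the only safeguard.** Table 1 and Section 5.3.4 also tell participants to avoid vulnerable contacts for two weeks after leaving.

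**Conclusion.** The contradiction is real and lies in current text. The Day 8 test is optional and exploratory in the schedule, and is stated as a discharge procedure in Section 8.17.2 and as confirmation before departure in Table 1. A site following the schedule literally could discharge a participant without it.

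The conflict involves one cell and one footnote reference, set against three passages, and Section 4.1 is silent on the test. It reaches every Day 8 discharge. How many participants would still be shedding then is not given, so no number can be put on the risk to contacts. The conclusion rests on two observations: nothing ranks the passages, and nothing links the Day 8 virology result to release. The matter has no bearing on sample size, power or type I error. It deserves correction because it concerns a stated control for a named third-party risk. It would be wrong to infer that making the test compulsory would by itself keep infectious participants in quarantine, since Section 1.1 leaves an extended stay to the Investigator.

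**What to change.** Reconcile the Day 8 schedule cell and footnote p with Sections 1.1, 2.3.1.3 (Table 1), 4.1 and 8.17.2, so that all give the same status and the same purpose for the test. There are two ways to reach consistency: align the schedule with the section text, or revise the statements in Table 1 and Sections 1.1 and 8.17.2 so that they no longer describe a confirmation that the schedule leaves optional. Section 4.1 should agree with whichever is chosen. Which rule applies is for the sponsor to decide.

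The cost is a short protocol amendment: one cell and one footnote reference under the first route, or a few sentences under the second. The test is already described in the protocol, so neither route adds a new procedure, and neither changes the statistical analysis.

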## 2. Introduction

SAB-176 is a purified human immunoglobulin G (hIgG) designed to specifically bind to Type A and Type B influenza viruses. The product is in development for use as a therapeutic agent to treat patients who are infected with Type A and Type B influenza viruses. The hIgG is purified from the plasma of immunized trans chromosomic (Tc) bovines that were immunized with a quadrivalent recombinant haemagglutinin (HA) protein vaccine produced in insect cells.

For more information on the non-clinical and clinical data regarding SAB-176, refer to the latest version of the Investigator's Brochure (IB Edition 1.2, 2021).

## 2.1. Background

Influenza causes substantial morbidity and mortality worldwide despite available antivirals and vaccines. Influenza is responsible for 226,000 excess hospitalizations and 30,000 to 50,000 deaths each year in the United States (US) alone (Thompson et al. 2003). Effective therapeutics are needed to prevent mortality or morbidity in those afflicted with severe influenza. Human plasma (delivered as Fresh Frozen Plasma units) or human intravenous immunoglobulin (hIVIg) with anti-influenza antibodies have been proposed as treatments for severe influenza (Luke et al. 2006). A limitation with plasma or hIVIg is that large numbers of human plasma donors/units must be screened to identify those few with a higher-than-average haemagglutination inhibition (HAI) titer to multiple strains of influenza. However, recent clinical trials have not shown benefit to hospitalized patients with severe Type A influenza infections treated with human-derived anti-influenza plasma or hIVIg (Beigel et al. 2019, Davey et al. 2019).

SAB Biotherapeutics, Inc., has developed SAB-176 to address the production limitations and lack of clinical efficacy of human-derived plasma or hIVIg. SAB-176 is a unique anti-influenza hIgG containing fully human polyclonal IgG antibodies with extremely high HAI and microneutralization titers against past, current, and potentially future strains of Type A influenza (H1N1/H3N2) and both lineages of Type B influenza (Yamagata/Victoria). SAB-176 is purified from the plasma of immunized Tc bovines that were immunized with a quadrivalent recombinant HA protein vaccine produced in insect cells. The HA antigens match the four influenza strains recommended yearly for the Northern hemisphere by the Center for Disease Control and Prevention.

Furthermore, Tc bovine hIgGs have an IgG1 subclass content of approximately 80-90% versus approximately 60% for human derived IVIg. IgG1 strongly activates complement and effector cells (natural killer cells, neutrophils, monocytes, etc.) of the innate immune system. SAB-176 is therefore much different than human-derived anti-influenza hIVIgs. SAB Biotherapeutics, Inc. believes that SAB-176's distinct attributes, in combination with early treatment of severe influenza disease, could demonstrate that the product reduces morbidity and mortality in patients with Type A and/or B influenza.

The genome of Tc bovines contains a human artificial chromosome comprising the entire human Ig gene repertoire (human Ig heavy chain [IgH] and human kappa light chain) that reside on two different human chromosomes (hChr), specifically the IgH locus from hChr14 and the immunoglobulin kappa (Igk) locus from hChr2. The system maintains the ability to use the genetic information provided by the immunoglobulin gene repertoires for generating the seemingly unlimited diversity of human polyclonal antibodies (pAbs).

Fully hlgG (hlgG/hlgĸ) can then be produced in these Tc bovines after vaccination with suitable antigens, and these animals produce up to 15 g/L of IgG antibodies in their plasma (similar to humans which have 7 to 16 g/L IgG). SAB-176 is an anti-influenza hlgG prepared in this system. Tc bovines receive repeated doses of a quadrivalent recombinant HA protein vaccine produced in insect cells. Just prior to immunization of the Tc bovine, the HA proteins are mixed with adjuvants.

Plasma is collected using an automated plasmapheresis system. After collection of sufficient volume, plasma undergoes Quality Control testing, is frozen and stored. Once it is ready to be processed, qualified frozen plasma is thawed, pooled, fractionated by caprylic acid and clarified by depth filtration in the presence of filter aid. The clarified sample containing hlgG is further purified by affinity chromatography, first using an anti-human IgG kappa affinity column to capture hlgG pAbs and remove residual non-hlgG and bovine plasma proteins. The sample is subsequently passed through an anti-bovine IgG heavy chain specific affinity column to further remove residual IgG molecules that contain a bovine heavy chain. The hlgG fraction is then subjected to a Q Sepharose chromatography polishing step to further reduce impurities, nanofiltration, final buffer exchange, concentration, and sterile filtration. Finally, the product is terminally filtered and filled into vials.

SAB-176 will be administered intravenously (IV) and will be diluted in saline.

## 2.2. Study Rationale

this study is to evaluate the safety and treatment efficacy of SAB-176 in a population inoculated with Influenza A/California/2009 H1N1 virus. This will both advance treatments for Type A and Type B influenza viruses, as well as establish the safety of the platform that could be used to quickly develop therapeutics for other emerging infectious diseases.

The Influenza A/California/2009 H1N1 virus challenge strain has been used for over 5 years by several groups globally and has helped assess influenza disease and therapies (Watson et al. 2015, Sloan et al. 2020). Specifically, hVIVO has direct experience with a range of H3N2, H1N1, and B influenza challenge viruses and have safety and inoculated over 1400 healthy participants, and specifically given over 100 participants a different batch of Influenza A/California/2009 H1N1 virus (Pleguezuelos et al. 2020).

The rationale for the study design is presented in Section 4.2.

## 2.3. Benefit/Risk Assessment

Healthy participants will not benefit from this clinical study. The study is designed to provide information about safety and efficacy of SAB-176.

More detailed information about the known and expected benefits and risks and reasonably expected adverse events (AEs) of SAB-176 may be found in the Investigator's Brochure.

#### 2.3.1. Risk Assessment

The known risks to participants are detailed in Table 1. However, there may also be risks that are unforeseen and not anticipated (e.g., unknown allergies). Every effort will be made to monitor the health of the participants to ensure that such risks are minimised. Trained medical personnel and facilities will be available to provide medical emergency care.

#### 2.3.1.1. Risks of SAB-176

SAB-176 is currently concluding a Phase 1 clinical trial (ClinicalTrials.gov identifier: NCT04471038). All participants have been infused with no serious adverse events (SAEs) reported through the highest dose cohort of 50 mg/kg and it appears to be safe and well tolerated. A previous Phase 1 study of SAB-301 (anti-Middle Eastern Respiratory Syndrome virus immunoglobulin) also derived from Tc bovines was shown to be safe and well tolerated at the highest dose of 50 mg/kg (ClinicalTrials.gov identifier: NCT02788188). It is anticipated that the risks for this Phase 2a study will be similar to the Phase 1 studies of SAB-176 and SAB-301 and the use of hIVIg with some unique considerations for proteins of animal origin as discussed below.

Based on hIVIg, common side effects may include:

- headache
- injection site reaction
- nausea
- urticaria
- fatigue
- arthralgia
- pyrexia.

Less common side effects may include:

- vomiting
- back pain
- rash.

Serious side effects seen with hIVIg that could be seen with SAB-176 include:

- Hyperproteinaemia, with resultant changes in serum viscosity and electrolyte imbalances may
  occur in patients receiving IVIg therapy (Steinberger et al. 2003). Humans routinely receive up to
  1 to 2 grams/kg of hIVIg to treat Guillain-Barre syndrome and other immune related neuropathies.
  Therefore, the addition of 50 mg/kg IgG as SAB-176 is a relatively small amount and is unlikely
  to cause AEs related to increased viscosity.
- Aseptic Meningitis Syndrome has been reported with IVIg treatments, especially with high doses or rapid infusion. This risk is anticipated to be minimized given the low amount of protein and relatively slow infusion.
- Haemolysis, either intravascular or due to enhanced red blood cell (RBC) sequestration, can be seen with human IVIg. This risk is anticipated to be low given the lack of exposure of the cows to human RBC antigens.
- Volume overload has been reported with human IVIg. This risk is anticipated to be minimized given the low amount of protein and small total volumes administered.

There may be additional risks of SAB-176 given its animal origin. SAB-176 is a fully human IgG so it is anticipated the risk would be less, though there may be residual animal proteins. The most similar product would be Horse Heptavalent Botulism Antitoxin which is an equine derived non-human polyclonal IgG polyclonal:

(http://www.fda.gov/downloads/BiologicsBloodVaccines/BloodBloodProducts/ApprovedProducts/Licensed ProductsBLAs/FractionatedPlasmaProducts/UCM345147.pdf),

There is the risk of off-target binding of the IVIg. In the worst case, this could cause immune activation (cytokine storm). The tissue cross reactivity assays do not predict any off-target binding, and this has not been seen in any other animal IVIg (of antigen-binding fragment [Fab]) preparations, so this risk is considered low.

For Horse Heptavalent Botulism Antitoxin, the most common adverse reactions (ARs) in all healthy participants were headache (9%), pruritus (5%), nausea (5%), and urticaria (5%). Other ARs reported in less than 4% of participants included pyrexia and throat discomfort. All reported ARs were considered mild or moderate. No serious ARs were reported. Two moderate acute allergic reactions that required premature termination of the infusion and treatment were reported. Reactions were predefined as mild if the participant was aware but could tolerate the symptoms. Moderate reactions were predefined as discomfort enough to interfere with normal daily activity.

The development of antibodies to bovine proteins and potential for food allergies is a theoretical concern. There is precedent for animal antibodies (or Fabs) being obtained from animal plasma and given to humans.

- Rabbit Anti-thymocyte Globulin [Thymoglobulin] (http://products.sanofi.ca/en/thymoglobulin.pdf).
- Horse Anti-thymocyte Globulin [Atgam] (http://www.fda.gov/downloads/BiologicsBloodVaccines/BloodBloodProducts/ApprovedProducts /LicensedProductsBLAs/FractionatedPlasmaProducts/UCM199603.pdf).
- Horse Heptavalent Botulism Antitoxin
   (http://www.fda.gov/downloads/BiologicsBloodVaccines/BloodBloodProducts/ApprovedProducts
   /LicensedProductsBLAs/FractionatedPlasmaProducts/UCM345147.pdf).
- Sheep Digoxin Immune Fab [DigiFab] (http://www.fda.gov/downloads/BiologicsBloodVaccines/BloodBloodProducts/ApprovedProducts /LicensedProductsBLAs/FractionatedPlasmaProducts/ucm117626.pdf).
- Sheep Digoxin Immune Fab [DigiBind] (http://dailymed.nlm.nih.gov/dailymed/archives/fdaDrugInfo.cfm?archiveid=19044).
- Sheep Crotalidae Polyvalent Immune Fab [CroFab] (http://www.crofab.com/documents/CroFab-Prescribing\_Information.pdf).

Upon review of these package inserts, the development of anti-drug antibodies (ADAs) was noted only in Horse Heptavalent Botulism Antitoxin (11 of 271 participants). There was no warning in any of these products concerning the development of allergies to other animal proteins, nor of any food allergies. As SAB-176 is a transgenic human IgG, the risk should be even further minimized. However, given that American / European diet is often heavy in bovine products (milk and/or beef, including derivatives), there is the risk of development of anti-bovine antibodies that is stimulated with repeated exposure. Given the data above and the lack of precedent for the development of food allergies after exposure to similar products, it is anticipated this risk with SAB-176 is very small.

Patients exposed to topical bovine thrombin products (previously used in surgical procedures e.g., fibrin glue) have developed antibodies towards bovine thrombin and contaminating bovine factor V; these antibodies can cross react with human clotting factors and may cause coagulopathy (Insight Flu IVIg Pilot Study Group 2016). In that series, postoperative coagulation abnormalities were more common in patients with antibodies to human coagulation proteins. SAB-176 clinical lots contain less than 5 ppm (parts per million) of bovine plasma proteins, but the clinical significance of this level of bovine contaminants is not known. Regardless, the serial assessment of prothrombin time/partial thromboplastin time (PT/PTT) in the study will monitor for any coagulation abnormalities in the participants receiving SAB-176.

As SAB-176 is bovine derived, it may contain galactose-alpha-1,3-galactose (alpha-Gal) glycosylation of the IgG. In other products, the alpha-Gal glycosylation has been shown to be the source of immune based hypersensitivity reactions. For example, the epidermal growth factor receptor inhibitor cetuximab is a monoclonal antibody with alpha-Gal glycosylation. Cetuximab, while a marketed product, has been associated with hypersensitivity reactions, including anaphylaxis. In most participants that had hypersensitivity reaction to cetuximab, IgE antibodies were present in pretreatment samples (Chung et al. 2008).

Lastly, SAB's Tc-bovine production system and the US cattle population have a negligible risk for transmissible bovine spongiform encephalopathy (BSE), also known as "Mad Cow Disease". Only three reported cases of BSE infection in cattle have been documented in the US in the last decade. Risk assessments for infectious diseases were completed on the production herd, and documented procedures are in place to reduce or eliminate certain infectious diseases in the production animals. All inputs (feed, medications, and vaccines) have been evaluated for the transmission of viral and BSE agents. The manufacturing process was also evaluated for the clearance and removal of viruses and BSE. Virus removal has been validated. The BSE Western blot analysis was done to demonstrate clearance and removal of prions.

There may be additional risks not apparent or predicted by preclinical testing.

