## 8.16. Blood Samples

A maximum volume of 550 mL of blood may be taken from each participant for any given 8-week period. If additional samples are required in excess of this amount, e.g., to monitor abnormalities, these will be collected at the discretion of the Investigator.

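### PT/APTT is not scheduled at Day 28 for completers, although serial PT/PTT is the named monitoring for a clotting risk; adding it is a cheap improvement

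*Combined protocol and SAP*

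**What the plan says.** Section 2.3.1.1 describes patients exposed to topical bovine thrombin who developed antibodies to bovine thrombin and to contaminating bovine factor V, and says that "these antibodies can cross react with human clotting factors and may cause coagulopathy". It puts residual bovine plasma protein in SAB-176 clinical lots below 5 ppm, but adds that "the clinical significance of this level of bovine contaminants is not known". The monitoring that it then names is that "the serial assessment of prothrombin time/partial thromboplastin time (PT/PTT) in the study will monitor for any coagulation abnormalities in the participants receiving SAB-176". No end date is given for that series.

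The Schedule of Activities (Section 1.2) marks coagulation at screening, Day -2/-1, Day 1, Day 3, Day 7, Day 8 in parentheses, and the early withdrawal visit. The Day 28 cell is empty. On parentheses, the notes to the schedule say: "Parenthesis indicates the assessment may be optional, or at the PI's discretion". The coagulation panel in Appendix 2 (Table 7) is PT and APTT.

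The haematology and biochemistry rows are both marked at Day 28. So is ADA blood, which follows the PK sampling times in Section 8.16.3. Section 9.4.7 plans to summarise coagulation with the other laboratory data by collection time and treatment group.

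**The concern.** The hazard described is an antibody response to the infused product, and PT/PTT is the test the protocol relies on to watch for it. For a completer, the last mandatory PT/APTT falls 6 days after infusion, while safety follow-up runs to Day 28. Planned discharge from quarantine is Day 8 and the next scheduled visit is Day 28, so close observation ends at about the same time as the clotting tests.

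At stake is a limited piece of safety information in healthy volunteers who get no direct benefit from the product. A prolongation of PT or APTT that first appeared after Day 7 or 8 and caused no symptoms would not be measured. The coagulation summary under Section 9.4.7 would stop at Day 7 or 8, while haematology and biochemistry continue to Day 28. No efficacy endpoint is involved.

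**Working it through.** The plan states no figure on this point to reproduce. The check is a comparison of schedule rows, followed by some simple arithmetic.

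**Reading the rows.** Each row in the extracted schedule has 16 cells and lines up with the 16 column headings. In the coagulation row the early withdrawal mark sits in the last column and the cell before it, Day 28, is empty, so the blank is unlikely to be an extraction fault.

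| Panel | Mandatory after infusion (completers) | Day 8 | Day 28 | Early withdrawal |
|---|---|---|---|---|
| Coagulation | Days 3, 7 | optional | none | yes |
| Haematology | Days 3, 7, 28 | optional | yes | yes |
| Biochemistry | Days 3, 7, 28 | optional | yes | yes |

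The Day 1 coagulation mark carries a superscript that is garbled in the extracted text. Note d concerns urine pregnancy tests, so note q (pre-infusion) is the sensible reading. If the Day 1 sample were taken after infusion, an early reading would be added and the last mandatory test would still be Day 7.

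**Timing.** Infusion is on Day 1.
- Day 3: 3 − 1 = 2 days after infusion.
- Day 7: 7 − 1 = 6 days.
- Day 8, if taken: 8 − 1 = 7 days.
- Day 28: 28 − 1 = 27 days, or 24 to 30 days with the ±3-day visit window.

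A Day 28 test would raise the mandatory post-infusion readings from 2 to 3 and move the last one from 6 to 27 days after infusion.

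**What existing provisions would catch.**
- A clinically significant PT/APTT abnormality already found by Day 7 or 8 is followed up (Section 10.3.6.1).
- Overt bleeding would be reported as an adverse event, collected to the last visit (Section 8.18.1).
- Day 28 includes a complete physical examination, urinalysis with dipstick blood, and haematology with haemoglobin and platelets (Section 1.2; Appendix 2).
- Extra tests may be done at the investigator's discretion (Section 8.16.1), and a safety review committee monitors continuously (Section 10.1.5).

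None of these measures PT or APTT in someone who is well and whose last result was normal. Follow-up starts from an abnormal result, a discretionary test needs a prompt, and a laboratory adverse event needs a measured deterioration (Section 10.3.6.2, Laboratory Values). ADA blood looks for antibodies to SAB-176 and is not stated to cover clotting factors.

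**What one Day 28 sample could show.** Assume 30 participants on SAB-176, all with a result. If none is abnormal, the one-sided 95% upper limit for the true rate is 1 − 0.05^(1/30) = 9.5%.

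Chance abnormal values also matter. Assuming 2.5% of unaffected people exceed the upper limit of one test, the chance of at least one high value among 30 is 1 − 0.975^30 = 53%. A Day 28 result is therefore interpretable mainly against the concurrent placebo arm.

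**Blood volume.** Section 8.16 states: "A maximum volume of 550 mL of blood may be taken from each participant for any given 8-week period". Assuming a 2 to 5 mL tube, the addition is 2/550 = 0.4% to 5/550 = 0.9% of that limit.

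**The case against.** The strongest reply is that this is a preference. Tests before infusion, on Days 3 and 7, and optionally on Day 8 are a series, and Section 2.3.1.1 promises no more than that. Panels may differ by design: cardiac enzymes also have no Day 28 mark. The hazard is thinly supported too. The example is topical bovine thrombin used in surgery, whereas SAB-176 is given once and is affinity-purified (Section 2.1). If ppm is relative to IgG mass, 50 mg/kg × 5 × 10⁻⁶ gives less than 0.25 µg/kg of all bovine plasma proteins together. No document says that thrombin or factor V is present. Phase 1 reported no serious adverse events up to 50 mg/kg.

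Most of this stands, and it sets the severity. A reader might infer that the schedule breaks a commitment made in the risk section, or that it stops before the hazard would appear. The documents support neither reading: no end date is promised and no onset time is given. The Investigator's Brochure, not available here, may explain the timing.

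The cardiac enzyme comparison is weaker than it looks. Table 1 ties those tests to viral myocarditis and states their timing of at least 3 and 7 days after challenge. No reason is given for ending coagulation at Day 7 or 8, and a participant who withdraws after Day 8 and attends the withdrawal visit would have a later PT/APTT than a completer.

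**Conclusion.** The point holds as a cheap improvement of the lowest severity. For completers, the test named for this hazard has no planned reading after Day 7, or Day 8 if the optional sample is taken. The other safeguards narrow the gap to a new, silent PT/APTT change arising after that time.

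This rests on reading the blank Day 28 cell as intended and Day 8 as optional. It does not rest on any assumed onset time, and the documents give no rate from which to estimate how often such a change would occur. Absolute risk is probably low after a single small exposure. Efficacy conclusions and the adverse event endpoints are unaffected.

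**What to change.** Mark PT/APTT at Day 28 in the coagulation row of the Schedule of Activities, drawn with the existing Day 28 bloods, and summarise it by arm under Section 9.4.7 against concurrent placebo.

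The cost is up to 60 extra PT/APTT assays (one per participant) and one small tube each, with no new visit or procedure. The total draw must stay within the 550 mL limit; the tube itself is under 1% of it on the assumption above. The change also needs a protocol amendment, with ethics committee approval before it is implemented (Section 10.1.1).

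The gain is limited. One sample would show a late change still present at Day 28 but would miss one that came and went after Day 8, and 0 of 30 abnormal would still be compatible with a true rate of up to 9.5%.
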